5.6. Analysis Visits

Analysis visit windows will be defined for by-visit summary and analysis purposes as illustrated in Table 5. Data not reported by-visit, including adverse events and concomitant medications, will not employ analysis visits. Analysis visit labels will be assigned to each post-baseline record (including records from unscheduled and early termination visits) based on the corresponding study day (relative to first study treatment or randomization if not treated). For post-baseline records collected outside the analysis visit window, a blank analysis visit label will be assigned. For example, a record collected at study Day 6 will not be utilized in any analyses or by visit descriptive summaries conducted at the OT or TOC scheduled visit. Descriptive summaries that are shown for “any assessment post baseline” e.g. maximum/minimum/ worst case post baseline, will use all assessments irrespective of whether they fall in an analysis visit window.

Table 5 Analysis Visit Windows

Post-Baseline Scheduled Visit	Protocol Window (Days)	Target Day	Analysis Visit Window (Days)
On-therapy	2 to 4	3	2 to 5

Post-Baseline Scheduled Visit	Protocol Window (Days)	Target Day	Analysis Visit Window (Days)
Test-of-Cure	10 to 13	12	9 to 16
Follow-up	25 to 31	28	21 to 31

If multiple records exist within the same analysis visit window, then the record occurring closest to the target day will be utilized in all analyses and analysis population determinations. If multiple records are equally close to the target day, then the later record will be utilized. If multiple records occur on the same day and time is not collected, then the record with the larger Study Data Tabulation Model (SDTM) record sequence number will be utilized in all analyses. All protocol assessments (including unscheduled and early termination visits) will be presented in subject Listings. Both the nominal and analysis visit will be presented in Listings.

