- b. For the On-therapy (Day 2 to 4) Visit: Participants will be instructed to return to the study site within 1 to 3 days postrandomization. Each treatment day will be assessed over 24 hours starting with the first dose of study treatment, as further detailed in the Study Reference Manual. For the TOC (Day 10 to 13) Visit: Participants will be instructed to return to the study site 5 to 8 days after completion of study treatment.
- c. At the TOC Visit, the physical examination may be symptom directed and is only required if indicated for a specific participant.
- d. Individual clinical signs and symptoms scores of acute cystitis will be recorded by a study physician or otherwise appropriately medically trained staff based on participant interview and using the scoring system in Appendix 6. The same scorer will be used at all assessment time points for each participant, on all occasions, whenever possible.

CCI

study physician or otherwise appropriately medically trained staff who performed the clinical scoring assessment.

- f. Based on confirmation of nitrite or pyuria (>15 WBC/HPF or the presence of 3+/large leukocyte esterase) from a pretreatment clean-catch midstream urine sample per local laboratory procedures.
- g. Participants will provide a clean-catch midstream urine sample at each visit for Gram stain, quantitative bacteriology culture, and in vitro antimicrobial susceptibility testing by a designated central laboratory(ies). Refer to the laboratory manual.
- h. A bacteriology urine sample will be collected at the On-therapy Visit, as further detailed in the Study Reference Manual.
- i. See Section 5.2 for ECG exclusion criterion for participants aged ≥ 12 to <18 years. For additional details see Section 7.1.2 and Section 8.2.3. Triplicate ECGs will be performed at Baseline. For the first approximately 1200 participants enrolled, On-therapy triplicate ECGs will also be obtained. The On-therapy ECGs will be collected at approximately 2 hours postdose (i.e., expected time of maximum concentration; ECG collection should ideally be within approximately 1.5 hours postdose to 4 hours postdose). After the first approximately 1200 participants have triplicate ECGs performed at On-therapy, the ECG collection at this visit is no longer a protocol requirement. Electrocardiograms will be reviewed locally by the investigator for safety purposes. Electrocardiograms will be centrally overread for the data analysis.

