- For the primary efficacy endpoint of therapeutic response (combined per-participant microbiological and clinical response), therapeutic success refers to participants who have been deemed both a microbiological success (reduction of all qualifying bacterial uropathogens [e.g., $\geq 10^5$ CFU/mL; defined in [Appendix 4](#)] recovered at Baseline to $< 10^3$ CFU/mL as observed on quantitative urine culture without the participant receiving other systemic antimicrobials) and a clinical success (resolution of signs and symptoms of acute cystitis present at Baseline [and no new signs and symptoms] without the participant receiving other systemic antimicrobials) at the TOC Visit in the Microbiological Intent-to-Treat Nitrofurantoin-Susceptible (micro-ITT NTF-S) Population, regardless of treatment discontinuation. The TOC Visit is 10 to 13 days after randomization, which is also 5 to 8 days after completion of study treatment.
- Participants may return to the study site at any time due to AEs or if they are experiencing new or continuing signs and symptoms of acute cystitis. Participants will be assessed and treated per the investigator's judgement. If a participant is switched to a different antibiotic before or during the TOC Visit, all TOC procedures should be completed before the other antibiotic is started.

- Participants with a concomitant fungal infection can only be treated with topical antifungals per local standard of care.
- Participants will return to the study site on Day 28 (± 3) for a Follow-up Visit. Participants experiencing signs and symptoms suggestive of infection recurrence or relapse will be assessed and treated per the investigator's judgement.
- The duration of study participation is approximately 28 days with 4 planned study visits (see Section 8 for study visit details):
 - Baseline (Day 1) Visit
 - On-therapy (Day 2 to 4) Visit
 - TOC (Day 10 to 13) Visit
 - Follow-up (Day 28 ± 3) Visit

A study design schematic is depicted in [Figure 1](#). The Schedule of Activities (SoA) is provided in [Section 1.3](#).

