- **Follow-up (Day 28±3) Visit.** Participants will be instructed to return to the study site 28 (±3) days postrandomization in order to complete the Follow-up Visit. Assessments will be performed as shown in Section 1.3, including the following:
 - The Follow-up Visit will be preceded by a documented reminder contact from the study site to the participant 24 ±4 hours before the scheduled appointment time per the method (e.g., text message, telephone call, e-mail) confirmed with the study site staff prior to departing the study site on Day 1.
 - Specimens for microbiological testing will be collected, as described in Section 8.1. Clinical signs and symptoms of acute cystitis will be recorded, as described in Section 8.1.3.1 and Appendix 6. CCI
[REDACTED]
[REDACTED]
 - Participants experiencing signs and symptoms suggestive of infection recurrence or relapse will be assessed and treated per the investigator's judgement.

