7.2.1. Endpoint / Variables

7.2.1.1. Microbiological Outcome and Response at TOC and Follow-up

The microbiological outcome and response are evaluated at participant level at the TOC and FU Visits. The criteria of uropathogen-level microbiological outcome and response are defined in Table 6 (TOC) and similarly in Table 9 (FU). The criteria of participant-level microbiological outcome and response are defined in Table 7 (TOC) and Table 10 (FU).

Table 9 Microbiological Outcome and Response by Baseline Qualifying Uropathogen at the Follow-Up Visit – Uropathogen Level

Defining Criteria	Outcome	Response
Participants considered microbiological failures at the TOC Visit will also be considered microbiological failures at the FU Visit.		
A quantitative urine culture taken at the Follow-up Visit shows reduction of the qualifying uropathogen recovered at Baseline to $<10^3$ CFU/mL following microbiological eradication at the TOC Visit, without the participant receiving other systemic antimicrobials before the Follow-up Visit	Sustained microbiological eradication	Microbiological success
A quantitative urine culture taken at the Follow-up Visit shows that the qualifying uropathogen recovered at Baseline grows $\geq 10^3$ CFU/mL following microbiological eradication at the TOC Visit, without the participant receiving other systemic antimicrobials before the Follow-up Visit	Microbiological recurrence	Microbiological failure
A quantitative urine culture taken at the Follow-up Visit shows that the qualifying uropathogen recovered at Baseline grows $\geq 10^3$ CFU/mL, and also did not achieve an outcome of microbiological eradication at the TOC Visit, without the participant receiving other systemic antimicrobials before the Follow-up Visit	Microbiological persistence	Microbiological failure
A quantitative urine culture taken at the Follow-up Visit shows reduction of the qualifying uropathogen recovered at Baseline to $<10^3$ CFU/mL, and also did not achieve an outcome of microbiological eradication at the TOC Visit, without the participant receiving other systemic antimicrobials before the Follow-up Visit	Delayed microbiological eradication	Microbiological failure
1) The FU urine culture result is missing or 2) The participant received other systemic antimicrobials before the FU Visit	Unable to determine	Microbiological failure

CFU=colony-forming units; TOC=Test-of-Cure.

Table 10 Participant-Level Microbiological Outcome and Response at the Follow-Up Visit

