11.4. Appendix 4: Derived and Transformed Data

11.4.1. General

Multiple Measurements at One Analysis Time Point

 The arithmetic mean of the three recorded ECG measurements will be employed as described in Section 8.4. Analysis visits will be created based on visit windows as described in Section 5.6. All assessments (including unscheduled and early termination visits) will be presented in subject listings. Participants having both High and Low values for Normal Ranges at any post-baseline visit for safety parameters will be counted in both the High and Low categories of “Any visit post-baseline” row of related summary Tables. This will also be applicable to relevant Potential Clinical Importance summary Tables.
Study Day

 Calculated as the number of days from First Dose Date (or Randomization Date if not dosed): 
 Ref Date = Missing → Study Day = Missing Ref Date < First Dose Date → Study Day = Ref Date – First Dose Date Ref Date ≥ First Dose Date → Study Day = Ref Date – (First Dose Date) + 1

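### SAP Table 5 gives the Follow-up Visit no late margin, so a record on Study Day 32, which one of the protocol's two wordings allows, is dropped and an observed cure can be counted as failure

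*SAP*

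**What the plan says.** SAP Section 5.6, Table 5 lists the Follow-up Visit with a protocol window of 25 to 31, a target day of 28 and an analysis window of 21 to 31. Labels follow study day, not the nominal visit. For anything else the rule is: "For post-baseline records collected outside the analysis visit window, a blank analysis visit label will be assigned". The SAP's own example, a Day 6 record, confirms that an unlabelled record enters no by-visit analysis. Section 11.4.1 defines study day: "Ref Date ≥ First Dose Date → Study Day = Ref Date – (First Dose Date) + 1".

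The protocol states the Follow-up timing in two ways:

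- Section 4.1, in line with the Synopsis and the Schedule of Activities: "Participants will return to the study site on Day 28 (± 3) for a Follow-up Visit".
- Section 8: "Participants will be instructed to return to the study site 28 (±3) days postrandomization in order to complete the Follow-up Visit".

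If there is no usable Follow-up record, SAP Table 9 applies ("The FU urine culture result is missing" is one of its criteria) and the microbiological response is failure. Table 11 does the same for a missing clinical assessment. Section 7.2.1.3 makes therapeutic response a failure unless both components are successes, and Section 11.5.2 repeats the missing-equals-failure rule.

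**The concern.** Follow-up is the last visit, so no later window can collide with it, and Section 5.6 gives no reason for stopping at Day 31. A participant with no symptoms and a negative culture on Day 32 has been observed to be cured, yet the rule treats her as unobserved and then as failed. The same findings on Day 21 would count as success if no record lay closer to Day 28.

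At stake are clinical, microbiological and therapeutic response at Follow-up, including Table 2.10, which SAP Appendix 9 lists as a headline deliverable. A relapse first seen on Day 32 would likewise generally be reported as undeterminable rather than as recurrence. The planned sensitivity analysis for these endpoints (SAP 7.2.6.2) only removes the stratification adjustment. The multiple imputation and tipping-point analyses (SAP 7.1.6.2) concern TOC. Nothing planned brings the late record back.

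**Working it through.** **1. The plan's own figure.** With Baseline as Day 1, Day 28 ±3 gives 28 − 3 = 25 and 28 + 3 = 31. This reproduces the protocol window of 25 to 31 in Table 5.

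**2. The Section 8 wording on the SAP scale.** The first dose is given at the Baseline Visit, so randomization and first dose are taken as the same date. Study Day = days postrandomization + 1.

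- Early end: 25 + 1 = Study Day 26.
- Late end: 31 + 1 = Study Day 32. This exceeds 31, so the label is blank.

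The protocol makes the same conversion for On-therapy in Schedule of Activities footnote b: "For the On-therapy (Day 2 to 4) Visit: Participants will be instructed to return to the study site within 1 to 3 days postrandomization". There 1 + 1 = 2 and 3 + 1 = 4.

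**3. The same shift at TOC.** Protocol Section 4.1 places TOC 10 to 13 days after randomization. By the formula that is Study Day 11 to 14, which the 9 to 16 analysis window absorbs. The Follow-up window does not absorb its shift.

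**4. Margins in Table 5.**

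| Visit | Protocol window | Analysis window | Extra days early | Extra days late |
|---|---|---|---|---|
| On-therapy | 2 to 4 | 2 to 5 | 2 − 2 = 0 | 5 − 4 = 1 |
| TOC | 10 to 13 | 9 to 16 | 10 − 9 = 1 | 16 − 13 = 3 |
| Follow-up | 25 to 31 | 21 to 31 | 25 − 21 = 4 | 31 − 31 = 0 |

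**5. A TOC success seen only on Study Day 32, with no record in Day 21 to 31.**

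- ITT and micro-ITT NTF-S: the outcome is *Unable to determine* and the response is failure, for the clinical and microbiological components and hence for therapeutic response.
- ME-FU and CE-FU (SAP Section 4): she lacks the required Follow-up data and is generally excluded, not failed.
- A TOC failure is unaffected in response, because she is already a failure at Follow-up.

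**6. Size, on assumed inputs.** Let *p* be the true Follow-up success rate and *l* the share of would-be successes seen only after Day 31. The reported rate is *p*(1 − *l*), so the loss is *p* × *l*. The documents give no value for *l*. The only Follow-up therapeutic rate in them is 5 of 8 gepotidacin participants (63%) in the Phase IIa study (protocol 2.1), so *p* = 65% is an assumption.

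- *l* = 2%: 0.65 × 0.02 = 1.3 points.
- *l* = 5%: 0.65 × 0.05 = 3.25 points.
- *l* = 10%: 0.65 × 0.10 = 6.5 points.

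Arm difference, gepotidacin minus nitrofurantoin:

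- True 70% v 65%, 5% late in both arms: 0.70 × 0.95 − 0.65 × 0.95 = 66.5 − 61.75 = 4.75 points, against a true 5.
- True 65% v 65%, 5% late v 2% late: 61.75 − 63.7 = −1.95 points, against a true 0.
- The same with the late shares swapped: +1.95 points.

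**The case against.** The strongest reply is that Day 32 is simply out of window. The Synopsis, the Schedule of Activities and Section 4.1 all say Day 28 ±3, and the Section 8 bullet that uses the postrandomization phrase carries Day 28 ±3 in its own heading. At TOC the protocol equates Day 10 to 13 with 10 to 13 days after randomization and with 5 to 8 days after treatment ends. If treatment ends on Day 5, that is 5 + 5 = 10 and 5 + 8 = 13. So in that place days after randomization means study day, the opposite of the On-therapy usage. This stands. A reader might infer that the SAP plainly fails protocol-compliant visits, but the documents support only that it does so under one of two inconsistent wordings.

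On the other wording the analysis window contains the whole protocol window, and crediting late visits is a prespecified choice. That is fair, but it does not explain why Follow-up alone has no late margin while gaining 4 early days.

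Other points also stand. Visits are booked on Day 1 and preceded by a reminder, which should limit lateness. Abstinence is requested only through TOC, so a later culture may reflect new exposure and is not clearly the more informative one. Listings show every record with both its nominal and its analysis visit, so late data remain visible.

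**Conclusion.** The point holds within limits. The Follow-up analysis window has no late margin, the protocol's two wordings differ by one day at exactly that edge, and an observed cure on Study Day 32 or later can be reported as failure in the ITT and micro-ITT NTF-S analyses. This needs a participant who succeeded at TOC, would have succeeded at Follow-up, and has no other record in Day 21 to 31.

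Three stronger inferences are tempting and not supported:

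- **Failure on every Follow-up analysis.** ME-FU and CE-FU generally exclude such participants.
- **The arm difference always shrinks toward zero.** That needs equal late shares in the two arms; unequal shares can move it either way.
- **The trial's conclusion is at risk.** The primary TOC endpoint is untouched, and the secondary endpoints carry no formal hypothesis test (SAP 7.2.6.1).

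The size is unknown. The losses of 1.3 to 6.5 points rest on assumed late shares of 2% to 10% and an assumed 65% success rate.

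**What to change.** Before unblinding:

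1. Reconcile the Follow-up wording in protocol Section 8 with SAP Table 5 so that both use one day count.
2. Extend the Follow-up analysis window in Table 5 to at least Study Day 32, and keep the rule that the record closest to Day 28 is used. A Day 32 record is 4 days from target, so it cannot displace one from Day 25 to 31, which is at most 3 days away.
3. Consider a longer late margin. Day 35 would mirror the 7 days allowed before target (28 − 21 = 7). That limit is a judgement, and it could instead be a prespecified sensitivity analysis that uses late Follow-up records.

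The cost is one number in Table 5 and a wording correction. No new data are needed and the primary analysis does not change. The downside is that a few later assessments enter the Follow-up analysis.

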5.7. Other Considerations for Data Analyses and Data Handling Conventions

Other considerations for data analyses and data handling conventions are outlined in the appendices:

Section	Component
Section 11.1	Appendix 1: Schedule of Activities
Section 11.2	Appendix 2: Study Phases and Treatment Emergent Adverse Events
Section 11.3	Appendix 3: Data Display Standards & Handling Conventions
Section 11.4	Appendix 4: Derived and Transformed Data
Section 11.5	Appendix 5: Reporting Standards for Missing Data
Section 11.6	Appendix 6: Values of Potential Clinical Importance
Section 11.7	Appendix 7: Division of Microbiology and Infectious Diseases Adult Toxicity Tables for Adverse Event Assessment
Section 11.8	Appendix 8: Abbreviations & Trademarks
Section 11.9	Appendix 9: List of Data Displays
Section 11.10	Appendix 10: Qualifying Uropathogen
Section 11.11	Appendix 11: Uropathogen Phenotype
Section 11.12	Appendix 12: Uropathogen Genotype
Section 11.13	Appendix 13: Uropathogen Grouping and Order Example

6. STUDY POPULATION ANALYSES

6.1. Overview of Planned Study Population Analyses

The study population analyses will be mainly based on the ITT Population and the primary analysis population (micro-ITT NTF-S/micro-ITT NTF-S (IA Set)), unless otherwise specified. Study population analyses including subject disposition, protocol deviations, demographic and baseline characteristics, prior and concomitant medications, and exposure and treatment compliance will be based on GSK Core Data Standards. Baseline disease characteristics including baseline clinical symptom score, baseline uropathogens (including phenotypic and genotypic subcategories), past and current medical conditions, history of uncomplicated UTI, and exposure data will also be summarized.

6.1.1. Disposition and Protocol Deviations

All participants who provided informed consent will be accounted for. Participant disposition will be tabulated for each treatment group and overall, with the number of participants who completed the study, or prematurely withdrew, with the reason for early withdrawal presented for the ITT and micro-ITT NTF-S Populations and micro-ITT NTF-S (IA Set) Population if the study stops for efficacy. Separately, a summary of treatment status and reasons for discontinuation of study treatment will be provided for each treatment group and overall, with the number of participants who completed treatment, or prematurely discontinued treatment, and the primary reasons for treatment discontinuation tabulated for the ITT and micro-ITT NTF-S Populations and micro-ITT NTF-S (IA Set) Population if the study stops for efficacy.

The number and percentage of participants enrolled by country and site will be summarized for each treatment group and overall for the ITT Population.

For the Screened Population, a summary of reasons for screen failure (did not meet inclusion/exclusion criteria, adverse event, protocol deviation, lost to follow up, investigator discretion, withdrew consent, or other) will be provided.

A Table will be produced summarizing the number of participants in each analysis population for all participants who provided informed consent. A separate Table will also be constructed that summarizes the reasons for exclusion from each study population for all participants in the ITT Population. For each study population, failure to meet specific study population requirements will be summarized by treatment group and overall. Note that only participants with pre-defined uropathogens [Gram-negative bacilli (e.g. *E. coli*, *K. pneumoniae*, *P. mirabilis*), *S. saprophyticus*, and *Enterococcus* spp. as described in Section 7.3.2] will be considered for inclusion in the relevant microbiological populations.

The number and percentage of participants in the ITT Population with significant protocol deviations will be summarized by category and coded term.

All data will be listed by participant (paginated by treatment group).

6.1.2. Demographic and Baseline Disease Characteristics

Demographic and other baseline characteristics such as age, sex, race, ethnicity, childbearing potential, height, weight, body mass index (BMI), baseline acute cystitis recurrence and baseline renal impairment category will be summarized and tabulated by treatment group and for all participants in ITT, micro-ITT NTF-S, CE-TOC, and ME-TOC NTF-S Populations and micro-ITT NTF-S (IA Set) Population if the study stops for efficacy. Descriptive statistics will be presented for age, height, weight, and BMI. Frequency counts and percentages will be presented for age category, sex, race, ethnicity, childbearing potential, and baseline acute cystitis recurrence. Age is computed as integer part of (First Dose Date - JUN30 of Collected Birth Year + 1)/365.25; when first dose date is missing, the informed consent date is used. Individual participant demographics (including baseline acute cystitis status) will be presented in Listings.

Baseline disease characteristics will summarize baseline quantitative bacterial counts, number of subjects with at least one baseline qualifying uropathogen identified, number of baseline qualifying uropathogens identified per subject, baseline qualifying uropathogens identified, and baseline clinical symptom score in ITT, micro-ITT and its derivatives (including micro-ITT NTF-S (IA Set) Population if the study stops for efficacy), CE-TOC, ME-TOC and its derivatives, ME-FU and its derivative populations. Separately, baseline uropathogens and qualifying uropathogens (including phenotypic and genotypic subcategories) will be summarized for ITT, micro-ITT and its derivatives, ME-TOC and its derivatives, ME-FU and its derivative populations. Baseline qualifying uropathogens will also be summarized separately by species and group (e.g., *Klebsiella* spp., other Enterobacteriales, gram-negative nonfermenters, gram-positive species) for micro-ITT and its derivatives, ME-TOC and its derivatives, ME-FU and its derivative populations. Data will be listed and summarized using descriptive statistics or frequency counts and percentages as applicable.

The severity of renal impairment will be evaluated using estimated by creatinine clearance (C_{Cr}) using the Cockcroft and Gault formula (1973):

$$C_{Cr}(\text{mL} / \text{min}) = \frac{((140 - \text{age}) \times \text{weight})}{72 \times \text{Scr}} \times 0.85$$

where

- Scr is serum creatinine in (mg/dL)
- Age in years
- Weight in kg

Severity of renal impairment will be categorized based on creatinine clearance as below (rounded to the nearest integer):

- Normal (≥ 90 mL/min)
- Mild (≥ 60 to 89 mL/min)
- Moderate (≥ 30 to 59 mL/min)
- Severe (< 30 mL/min)

Substance use such as smoking history, cigarettes per day, alcohol consumption, alcohol weekly use, caffeine consumption, and average caffeinated servings per day will also be summarized and listed.

The details of data displays are presented in [Appendix 9](#)

